3. STUDY POPULATION

3.1. DESCRIPTION OF THE POPULATION

This study is intended for patients over the age of 75 who have undergone surgery for a fracture of the upper end of the femur.

3.2. INCLUSION CRITERIA

- Patients aged 75 years and older, regardless of gender.
- Patients who have undergone surgery for a fracture of the upper end of the femur.
- Patients, family members or trusted relatives who do not object to participation in the study
- Patients affiliated with a social security scheme
- Patients who can be monitored within the framework of the protocol

3.3. EXCLUSION CRITERIA

- Refusal to participate in the study (patient, family or trusted relative)
- Patient with weight-bearing on the operated limb not authorised by the surgeon
- Patient with an associated fracture (multiple trauma, concomitant trauma to the upper limb, etc.)
- Patient with a pathological fracture
- Patient included in a category 1 interventional study (involving a drug or medical device)
- Patient deprived of liberty
- Patients not affiliated with a social security scheme

4. STUDY DESIGN AND PROCEDURE

4.1. STUDY SCHEDULE

The inclusion period will be 42 months. Follow-up is 6 months post-operative.

Patients may be included up to 48 hours after their arrival in the orthopaedic/orthopaedic surgery department.

a. D0 - Arrival in the orthopaedic/orthopaedic surgery department (after surgery)

Provision of the information leaflet and collection of non-objection after a reflection period.

Completion of the ASA score (*investigator*)

Biological tests (complete blood count (CBC), CRP, ferritin, transferrin saturation coefficient, albumin, vitamins B12, folate and vitamin D) (*investigator – performed on arrival at A&E or on admission to the department before surgery*)

Record of severe fractures prior to inclusion: upper end of the femur or humerus, proximal tibia, distal femur, 3 simultaneous ribs, wrist, pelvis and spine (Grio 2011 recommendations) (*investigator*)

Screening for previous or current upper function disorders (*investigator*)

Screening for major sensory disorders (*investigator*)

Completion of ADL and IADL questionnaires: **information relating to the week preceding the intervention** (*investigator: interview with patient, family or staff of residential care homes for elderly dependents (EHPAD)*)

Completion of the CIRS-G score (*investigator*)

Completion of the CAS questionnaire

Recording of lifestyle and living environment (*investigator*)

Number of medications (by class) taken by the patient on admission (anticoagulants, antiplatelet agents, NSAIDs, anti-osteoporotics, analgesics) (*investigator*) Completion of the MiniGDS score (*investigator*)

Collection of data on the procedure: time to surgery, type of fracture, surgical procedure, type of anaesthesia, weight-bearing authorisation, transfusion, number of red blood cell units received Haemoglobin measurement (if different from that taken in the emergency department or on admission to the ward before the procedure)

b. During the hospital stay: (trained orthopaedic nurses)

CAS score performed on days 1 to 3 post-operative, as well as on day 5 (or on discharge if this occurs before day 5)

Daily screening for confusion (CAM) until D10 if the patient is still hospitalised Completion of ADL questionnaires (*patient, family or nursing home resident interview*) on D5 post-operative (or on discharge if this occurs before D5)

Measurement of grip strength – Hand Grip on day 5 (or upon discharge if this occurs before day 5)

Record of falls occurring during hospitalisation

Record transfusions and number of red blood cell concentrates Measure haemoglobin levels on days 1, 3, 5, 10 and 15 after surgery

Recording of Venofer® administration on day 5 (or on discharge if this occurs before day 5)

Recording of post-operative complications: post-operative infection requiring antibiotic therapy (surgical site, pulmonary, urinary, skin, other), acute urinary retention requiring catheterisation, dislocation/loosening of prosthesis, iron deficiency (ferritin < 30 µg/L or CRP > 20 µg/L)

requiring urinary catheterisation, dislocation/loosening of prosthesis, iron deficiency (ferritin < 30 µg/L or CRP > 20 mg/L associated with a transferrin saturation coefficient < 15%) and/or vitamin deficiency (B12 < laboratory threshold, B9 (folate) < 3.5 ng/mL), cardiovascular/neurological complications, post-operative bleeding (including local and digestive), reoperation, haematomas.

Prescription for haemoglobin monitoring on days 5, 10 and 15 post-operatively if the patient has been discharged from hospital

Time allowed for completion: +/- 2 days

c. At the end of hospitalisation: (investigator)

Number of medications (by class) (anticoagulants, antiplatelet agents, NSAIDs, anti-osteoporotics, analgesics)

Screening for current higher brain function disorders Record of length of hospital stay

Record of discharge status

Record of vital status

d. Follow-up telephone call 1 month and 3 months post-operative (supplemented if necessary by questioning the patient, family or nursing home staff)

Record of living arrangements and location

Completion of ADL and IADL

questionnaires Completion of CAS

questionnaire

Investigation of late post-operative complications: infection requiring antibiotic treatment (surgical site, pulmonary, urinary, skin, other), acute urinary retention requiring urinary catheterisation, dislocation/loosening of prosthesis, cardiovascular/neurological complications, reoperation.

Record of recurrent falls or fractures New

hospitalisation and reason for hospitalisation Record of

vital status

e. Telephone follow-up 6 months post-operative (supplemented if necessary by questioning the patient, family or nursing home staff)

Record of lifestyle and living arrangements

Completion of ADL and IADL questionnaires

Completion of CAS questionnaire

Search for late post-operative complications: infection requiring antibiotic treatment (surgical site, pulmonary, urinary, skin, other), acute urinary retention requiring urinary catheterisation, dislocation/loosening of prosthesis, cardiovascular/neurological complications, reoperation.

Record of recurrent falls or fractures New

hospitalisation and reason for hospitalisation

Number of medications (by class) taken by the patient (anti-osteoporotic, analgesic) Vital status record

STUDY TIMELINE					
Actions	D Arrival in the orthopaedic surgery department (day of surgery)	From D1 to D4 post-op.	Day 5 post-op**	End of hospitalisation	M1, M3 and M6 post-op (+/- 15 days) Telephone follow-up
Information for patient/family/trusted relative Collection of non-objection form	X *				
ADL	X ¹		X		X
IADL	X ¹				X
CAS	X ¹	X (from D1 to D3)	X		X
HandGrip Test			X		
ASA score/CIRS-G score/MiniGDS score	X				
Confusion screening (CAM)		X (daily – up to day 10 if patient is still hospitalised)			
Screening for previous or current higher brain function disorders	X			X	
Check for major sensory disorders	X				
Haemoglobin	X	X (D1, D3, D5, D10, D15)			
NFS, CRP, albumin, ferritin, transferrin saturation coefficient, vitamins B12, folates and vitamin D	X				
Information about the procedure ²	X				
Post-operative complications		X (daily) ³			X ⁴
Fractures/falls	X (fractures)	X (daily)			X
Length of hospital stay/Discharge status				X	
Re-hospitalisation and reason					X
Concomitant treatments	X ⁵	X (End of hospitalisation) ⁵			X(M6) ⁶
Vital status		X	X	X	X

* Can be performed up to 48 hours after arrival at the department

** Five days after surgery or upon discharge from hospital if this occurs before five days

¹: Information relating to the week preceding the operation

² : Time of surgery, type of fracture, surgical procedure, type of anaesthesia, weight-bearing authorisation, transfusion, number of red blood cell units received

³ : Post-operative infection requiring antibiotic treatment (surgical site/pulmonary/urinary/skin/other), acute urinary retention requiring urinary catheterisation, dislocation/loosening of prosthesis, iron and/or vitamin deficiencies, transfusion, number of packed red blood cell units received, cardiovascular/neurological complications, post-operative bleeding (including local and digestive), reoperation, haematomas,

⁴ Infection requiring antibiotic therapy (surgical site/pulmonary/urinary/cutaneous/other), acute urinary retention requiring urinary catheterisation, dislocation/loosening of prosthesis, cardiovascular/neurological complications, repeat surgery,

^{4b}: anticoagulants, antiplatelet agents, NSAIDs, anti-osteoporotic agents, analgesics

⁶: anti-osteoporosis drugs, analgesics

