2.1.2. Primary evaluation criterion

- Haemoglobin level on day 5 post-operatively (considered the post-operative haemoglobin reference level in this study)
 - In the case of patients who received a transfusion postoperatively, the reference haemoglobin level will be the haemoglobin level at the end of hospitalisation
- Change in the Activities of Daily Living (ADL) score pre-fracture and 6 months post-operatively.
A loss of independence will be defined as a decrease of one point or more in the ADL.

The reference value for haemoglobin levels was arbitrarily set at 5 days post-operatively. This is because haemoglobin levels recorded in A&E or on admission to the ward prior to surgery, or immediately post-operatively, may be influenced by factors other than isolated anaemia. Dehydration, present in the emergency department or on admission to the ward before the operation, corrected preoperatively, and postoperative haemodilution due to fluid replacement, cause the haemoglobin level to vary without there being any real deglobulation. We therefore postulate that the haemoglobin level on the 5th postoperative day can serve as a reference.

Confounding factors collected

All confounding factors related to loss of autonomy will be collected:

- Transfusion and number of red blood cell concentrates received

The indication for transfusion is at the discretion of the prescriber. However, it is generally accepted to transfuse patients with haemoglobin levels below 8 g/dL, or below 10 g/dL in cases of ischaemic heart disease or poor clinical tolerance.

- Age
- Gender
- Height, weight, Body Mass Index (BMI) calculation
- Screening for past or present higher brain function disorders
- Screening for major sensory disorders
- Screening for depressive symptoms: Mini Geriatric Depression Scale (MiniGDS)
- Comorbidities assessed using the Cumulative Illness Rating Scale - Geriatrics (CIRS-G)
- ASA score
- Number of medications (per class) taken by the patient (anticoagulants, antiplatelet agents, NSAIDs, anti-osteoporotic drugs, analgesics)

- Lifestyle and living environment
- Severe fractures before and after inclusion
- Other falls during the year
- Protein-energy malnutrition
- Iron deficiency (ferritin < 30 µg/L or CRP > 20 mg/L associated with a transferrin saturation coefficient < 15%)
- Recurrence of falls at 1, 3 and 6 months post-op

2.2. *SECONDARY OBJECTIVES AND EVALUATION CRITERIA*

2.2.1. *Secondary objectives*

The secondary objectives are to analyse:

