- the influence of post-operative anaemia:
 - on independence in elderly patients who have undergone surgery for a fracture of the upper end of the femur upon discharge from hospital, at 1 month and 3 months post-operatively
 - on mortality 6 months after surgery
- the progression of post-operative anaemia

2.2.2. *Secondary evaluation criteria*

- Lowest postoperative haemoglobin level recorded on admission to the emergency department, on admission to the ward, on D0 (day of surgery), D1, D3, D5, D10 and D15 (postoperative days).
The severity of anaemia will be defined as follows:
 - greater than 12 g/dL,
 - less than or equal to 12 g/L
 - less than or equal to 8 g/L
 - less than 8 g/dL (and therefore requiring a transfusion)
- Assessment of Activities of Daily Living (ADL): pre-fracture, on day 5 post-operative (or on discharge from hospital if discharged before day 5) at 1 month, 3 months and 6 months post-operative.
- Assessment of instrumental Activities of Daily Living (IADL): pre-fracture, at 1 month, 3 months and 6 months post-operative.
Loss of independence will be defined as a decrease of one point or more in the ADL and/or IADL.
- Vital status at 6 months post-operatively

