4.3. DESCRIPTION DETAILED OF THE EVALUATION AND THE DATA COLLECTED

a. On patient autonomy:

- **Activities of Daily Living (ADL)** (21): Measured at inclusion (information relating to the week preceding the procedure) (questioning of patient, family, nursing home staff), on day 5 post-op (or on discharge from hospital if discharged before day 5) (*in hospital*), 1 month, 3 months and 6 months post-op (*telephone call*).

Validated scale for assessing independence in simple activities of daily living: hygiene, dressing, mobility, going to the toilet, continence, eating. Each item is coded as follows:

1: done independently

0.5: done partially or with assistance

0: not done

Scale ranging from 0 to 6, with a high score indicating a more independent patient.

- Lawton's 4-item **Instrumental Activities of Daily Living (IADL)** (22): Measured at inclusion (information relating to the week preceding the intervention) (questioning of patient, family, nursing home staff), at 1 month, 3 months and 6 months post-operatively (*telephone call*).

Validated scale for assessing patient autonomy in so-called "instrumental" activities of daily living: managing finances, preparing medication, using the telephone, using transport. Each item is coded as follows:

1 : done alone

0.5: does partially or with assistance

0: does not do

The score ranges from 0 to 8. A high score indicates that the patient is independent. This score can only be interpreted for subjects living at home.

- **Cumulative Ambulation Score** (23): Measured at inclusion (information relating to the week preceding the procedure), from D1 to D3 post-operative, on D5 post-operative (or on discharge if before D5) (*in-hospital*), and at 1 month, 3 months and 6 months (*telephone call*)

Validated score predictive of mortality, morbidity and rehabilitation. Three areas (transfer from lying to sitting, transfer from sitting to standing, walking with appropriate aids) are assessed from 0 (unable despite the help of two people) to 2 (able to do independently). The scores are cumulative over the first 3 days post-operatively and give a score of 0 to 18. A cumulative score greater than 10 corresponds to a 99% probability that the patient will be alive at one month, 93% that they will have returned home, and 94% that they will not have had any major post-operative complications.

b. On the patient's physical performance:

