4.4. SPECIAL SITUATIONS

Dementia patients: the interview with dementia patients will be completed by their family or nursing home staff. Information about participation in the study will be provided to the family/trusted relative.

If surgery is postponed (due to the patient's general condition or the presence of antiplatelet or anticoagulant treatment, for example), D0 remains the date of the procedure and corresponds to the patient's return to the orthopaedic/orthopaedic surgery department (after the procedure).

If the patient is discharged early, a standardised prescription will allow haemoglobin to be monitored on D5, D10 and D15 (timeframe: +/- 2 days).

A patient may receive a transfusion,

- pre- or peri-operative transfusion in the recovery room
- post-operative transfusion
 - In hospital: during the orthopaedic stay
 - Post-hospital: new hospitalisation required for transfusion

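### The baseline ADL is defined as pre-fracture but collected for the week before surgery, so losses of independence can be under-counted, more so when surgery is delayed

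*Combined protocol and SAP*

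**What the plan says.** Section 2.1.2 defines the primary outcome as "Change in the Activities of Daily Living (ADL) score pre-fracture and 6 months post-operatively", with the event set out as "A loss of independence will be defined as a decrease of one point or more in the ADL". Section 2.2.2 uses the same reference state for the secondary criteria: "Assessment of Activities of Daily Living (ADL): pre-fracture, on day 5 post-operative", and likewise for the IADL.

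The sections that tell sites what to ask use another window:

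- Section 4.1.a, for the ADL and IADL questionnaires: "information relating to the week preceding the intervention".
- Footnote 1 of the timeline table, attached to ADL, IADL and CAS: "Information relating to the week preceding the operation".
- Section 4.3.a, for the ADL: "Measured at inclusion (information relating to the week preceding the procedure". The IADL and CAS entries there are also anchored to surgery.

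Section 4.4 foresees delay, "If surgery is postponed (due to the patient's general condition or the presence of antiplatelet or anticoagulant treatment, for example", and keeps D0 at the date of the procedure. Section 4.3.c records time to surgery, counted from admission to the emergency department or ward. That variable is not in the confounder list of section 2.1.2, and no analysis in section 5.2 is tied to it.

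**The concern.** The fracture comes before the operation, so a week counted back from the operation contains the days lived with an unrepaired hip fracture. Hygiene, dressing, mobility and toileting are four of the six ADL items, and the fracture can be expected to affect them. A baseline lowered in this way shrinks the measured drop to 6 months, and the event is a drop of only one point on a 0 to 6 scale.

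The same baseline feeds the day-5, 1-month and 3-month ADL analyses and the IADL change. In a multicentre study there is a further risk: some interviewers may work from the pre-fracture label and others from the surgery-anchored instruction, so the baseline may not mean the same thing at every site.

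**Working it through.** **1. The two windows.** The criteria (2.1.2, 2.2.2) refer to the state before the fracture. The collection instructions (4.1.a, footnote 1, 4.3.a) refer to the seven days before surgery. The two match only if fracture and surgery fall close together. No section tells the interviewer to score only the days before the fracture, or how to score a week in which function changed.

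**2. Overlap.** With *d* days from fracture to surgery (*d* up to 7), the share of the window spent with the fracture is *d*/7.

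**3. Effect on the score (illustration).** Assumed, not in the documents: true pre-fracture ADL 6, ADL between fracture and surgery *F* = 1 to 3, and an interviewer who averages over the week. The baseline is then too low by *d*(6 − *F*)/7, and a true loss is counted only if it is at least 1 plus that amount.

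| *d* | Share of window | Baseline too low by | Smallest true loss counted (half-point steps) |
|---|---|---|---|
| 1 | 14% | 0.43 to 0.71 | 1.5 to 2 |
| 2 | 29% | 0.86 to 1.43 | 2 to 2.5 |
| 4 | 57% | 1.71 to 2.86 | 3 to 4 |
| 5 | 71% | 2.14 to 3.57 | 3.5 to 5 |

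At one day a true loss of exactly one point is missed, but every loss of two points or more is still counted. At five days the averaged baseline is 2.43 to 3.86, and a patient at ADL 1 at 6 months is still counted as a loss (2.43 − 1 = 1.43). Patients who were already dependent are affected less: with true ADL 4 and *F* = 3, the baseline is too low by 0.29 at two days and 0.71 at five.

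**4. Event count (illustration).** The plan's figure comes first: 210 per year × 1.5 years = 315, and 315 × 0.9 × 0.9 = 255.15, which is the stated 255. Section 5.2.2 cites 67.8% regaining prior independence, a 12-month figure, so the implied events are 255 × (1 − 0.678) = 82.1. That supports 8 model terms at 10 events each. If 10%, 20% or 30% of true losses were missed (assumed), the events would be 73.9, 65.7 or 57.5, supporting 7, 6 or 5 terms.

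**5. Association (illustration).** Inputs: 65% anaemic (the section 5.2.2 figure for below 10 g/dL) and an assumed true loss of 36% in anaemic and 25% in other patients. The overall rate is 0.65 × 0.36 + 0.35 × 0.25 = 0.3215, close to 32.2%. The true odds ratio is (0.36/0.64)/(0.25/0.75) = 1.69. Suppose also that every loss in an affected patient is hidden, which step 3 shows is too severe.

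| Affected: anaemic / other (assumed) | Observed loss | Odds ratio |
|---|---|---|
| 10% / 10% | 0.324 / 0.225 | 1.65 |
| 10% / 5% | 0.324 / 0.2375 | 1.54 |
| 15% / 5% | 0.306 / 0.2375 | 1.42 |

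In the last row the overall event rate is 0.65 × 0.306 + 0.35 × 0.2375 = 0.282. Equal misclassification barely moves the odds ratio. A sizeable shift needs the affected share to differ by anaemia status, and nothing in the documents supplies that.

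**The case against.** The best defence is that sites may record the right state anyway. The endpoint is named pre-fracture, and the informants include family and care-home staff, who mainly know how the patient functioned before admission. The appendices with the scales and the data-collection forms are listed but were not available for this review, so the questionnaire wording may be clearer. This stands as a limit on the claim: losses can be hidden, and it is not shown that they are. It does not remove the mismatch, because sections 4.1 and 4.3 are what interviewers follow, and section 5.1.3 has the data-entry forms built in accordance with the protocol.

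A reader might go further and infer that a previously independent patient will be scored as largely dependent, so that any 6-month value looks like stability or gain. The documents do not support this. No rule for a mixed week is given, and under averaging large losses are still counted even after five days.

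A reader might also infer that the anaemia association is biased towards the null. Section 4.4 names general condition and antiplatelet or anticoagulant treatment as reasons for delay, but says nothing about haemoglobin. The link is plausible and remains conjecture.

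**Conclusion.** The inconsistency is in the text and concerns the baseline of the primary outcome. The stated collection rule, followed literally, can lower that baseline and under-count losses of at least one point. Under averaging, this mainly affects losses near the threshold and patients with longer delays. Nothing in the planned analysis corrects it.

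The size is unknown. The documents give no distribution of time to surgery, and the event counts and odds ratios above rest on assumed shares, assumed loss rates and, for the odds ratios, the assumption that every loss in an affected patient is hidden. They show how the error would act and do not estimate it. Bias in the association beyond a small attenuation depends on a relation between delay and haemoglobin that the documents do not show. The case for correction is that the primary baseline carries two definitions and that aligning them costs very little.

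**What to change.** In section 4.1.a, footnote 1 of the timeline table, and the ADL, IADL and CAS entries of section 4.3.a, replace the surgery-anchored window with *the week preceding the fracture, whatever the time to surgery*. Put the same wording on the eCRF and send sites a short note.

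For patients already included, add a sensitivity analysis of the primary outcome that excludes, or stratifies by, long recorded time to surgery. State its limit: that clock starts at admission (section 4.3.c), so it misses any time between fracture and admission. A retrospective check against medical notes is not a workable substitute, because section 4.6 lists ADL, IADL and CAS among the source data not held in the medical record.

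The cost is slightly longer recall for the informant and one extra analysis. No visit, test or informant is added.

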However, to our knowledge, no study has examined the association between the recovery of overall functional autonomy, as measured by ADL, and the post-operative haemoglobin level in the very elderly. The aim of these analyses is to improve our understanding of the loss of autonomy observed post-operatively following FESF, especially in the longer term, in order to manage it as effectively as possible. For example, at the Centre Hospitalier Départemental (CHD) in La Roche sur Yon, it would be interesting to optimise the transfusion protocols adopted within the hospital. There are also patient profiles where functional autonomy, and the resulting quality of life, is more important than mortality alone (in very elderly patients, for example, or those with multiple comorbidities). Furthermore, in our department, anaemia is a factor that limits patient mobility (sitting in a chair, physiotherapy), which probably has consequences for their early and future autonomy. The database could be used to set up interventional studies seeking to limit this loss of autonomy.

In this study, we therefore propose to evaluate the impact of post-operative anaemia on the functional recovery of very elderly patients following surgery for a fracture of the upper end of the femur.

1.2. *BENEFITS AND RISKS FOR THE PEOPLE PARTICIPATING IN RESEARCH*

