4.5. REASON FOR THE TELEPHONE CALL

This study is aimed at elderly and often frail patients. The participating centres are referral centres that treat patients from all regions. For the most optimal and objective recovery possible, the 1-month, 3-month and 6-month assessments should have taken place during a geriatric consultation. Due to the likely frailty of the patients, the absence of systematic post-hospitalisation surgical consultations, and the sometimes significant distance from the patients' place of residence, we felt it was reasonable to limit this follow-up to a telephone follow-up, either with the patient, their family or the nursing staff at the nursing home. Thus, the telephone assessments are based on simple criteria that can be assessed over the phone.

It should be noted that follow-up, including autonomy, was also carried out by telephone during the study by Halm et al. (19).

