5. DATA MANAGEMENT AND STATISTICS

5.1. *COLLECTION AND PROCESSING OF STUDY DATA*

5.1.1. *Data collection*

An electronic case report form (eCRF) will be created for each patient. All information required by the protocol must be provided in the eCRF. It must include the data necessary to confirm compliance with the protocol and all data necessary for statistical analysis; it must allow for the detection of major deviations from the protocol.

The person(s) responsible for completing the eCRF (investigator, ARC, etc.) must be defined and identified in the table of delegated responsibilities for each centre (kept in the investigator's binder).

5.1.2. *Data coding*

By signing this protocol, the principal investigator and all co-investigators undertake to keep the identities of the patients who participated in the study confidential.

Each patient included in the study will be assigned an incremental code consisting of the following three items: treatment centre number, serial number, initials (first letter of surname and first letter of first name).

This code will be the only information that will appear on the electronic case report form (eCRF) and will enable the eCRF to be linked to the patient at a later date.

The investigator is also required to code patient data on all documents in their possession (imaging reports, biology reports, etc.) that are attached to the eCRF.

5.1.3. *Data processing*

Clinical data collection will be based on the establishment of a database and the creation of data entry forms modelled on the observation log, in accordance with the protocol and regulations currently in force.

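### The plan neither names the person who scores ADL by telephone at 6 months nor keeps haemoglobin and transfusion data from that person, so scoring of the primary outcome could depend on the exposure

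*Combined protocol and SAP*

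**What the plan says.** **Outcome.** Section 2.1.2 sets the primary event: "A loss of independence will be defined as a decrease of one point or more in the ADL", comparing pre-fracture with 6 months. Section 4.3.a describes six items, each coded 1, 0.5 or 0, with the middle code given as "0.5: done partially or with assistance". The total is a "Scale ranging from 0 to 6, with a high score indicating a more independent patient".

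**Exposure.** Section 2.1.2 uses "Haemoglobin level on day 5 post-operatively (considered the post-operative haemoglobin reference level in this study", replaced by the end-of-stay value in patients transfused after surgery. Either value exists months before the 6-month call.

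**Who scores.** Section 4.1 gives a role for the day-0 items (investigator), the hospital stay (trained orthopaedic nurses) and the end of the stay (investigator). For the 1-, 3- and 6-month calls it gives none; the last is headed "Telephone follow-up 6 months post-operative (supplemented if necessary by questioning the patient, family or nursing home staff". Section 4.5 explains the choice of telephone: "we felt it was reasonable to limit this follow-up to a telephone follow-up, either with the patient, their family or the nursing staff" of the nursing home. It accepts that a geriatric consultation would have been more objective, but does not discuss what the caller knows.

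**Who sees what.** Section 5.1.1 provides one eCRF per patient for all protocol data. "The person(s) responsible for completing the eCRF (investigator, ARC, etc.) must be defined" and listed in each centre's delegation table. Sections 4.1 to 4.5, 5.1 and 5.2 contain no masking of the caller.

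**Expectation.** Section 1.1 says, of the authors' own department, that "anaemia is a factor that limits patient mobility", and that later autonomy probably suffers as a result.

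**The concern.** Pre-fracture ADL is scheduled at inclusion, before the day-5 haemoglobin exists. The 6-month score is taken after it. Knowledge of the exposure can therefore enter the change score mainly at its second end, and a shift there does not cancel against the baseline.

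The respondent describes what the patient does and the caller turns that into 1, 0.5 or 0. In a patient whose ADL is unchanged, two half-step downgrades, or one full step, create an event. In a patient already half a point down, one half-step is enough.

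If such coding choices vary with the known haemoglobin or transfusion history, the error in the outcome differs by exposure. The confounder model in section 5.2.1 cannot correct that, because the error lies in the outcome and not in an omitted covariate. Section 1.2.1 says the study should lead to a standardised management protocol, including a transfusion strategy, so a distorted association would have practical consequences. The 1- and 3-month calls, which feed the secondary ADL analyses, are open to the same problem.

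**Working it through.** **Inputs (section 5.2.2).** 255 analysed; 65% with post-operative haemoglobin below 10 g/dL; 67.8% regaining previous independence, so loss = 1 − 0.678 = 0.322. That last figure is a 12-month result from a cited cohort and stands in for 6 months. Section 5.2.3 sets 5%; I take it as two-sided.

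**The plan's own figure.** 320 × (1 − 0.10 − 0.10) = 256. Alternatively, 18 months at 210 a year is 315, and 315 × 0.9 × 0.9 = 255.15. The stated 255 is reproduced. Expected events: 255 × 0.322 ≈ 82. The plan gives no power figure.

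**Groups.** 255 × 0.65 ≈ 166 below 10 g/dL and 255 − 166 = 89 at or above. The 10 g/dL split is used because it is the only one with a stated frequency; section 5.2.1 does not say in what form haemoglobin enters the logistic model.

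**Assumption.** The true loss rate is 0.322 in both groups (true odds ratio 1). A share x of anaemic patients without loss is scored as loss, and nobody else is misclassified. The documents give no value for x; 2%, 5% and 10% are chosen to show a range.

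**Formulas.**
- Observed rate in the anaemic group: p1 = 0.322 + 0.678x; other group p0 = 0.322
- Odds ratio = [p1/(1 − p1)] / [0.322/0.678]
- Pooled rate p̄ = (166·p1 + 89·0.322)/255; SE = √[p̄(1 − p̄)(1/166 + 1/89)]
- Rejection probability = Φ(d/SE − 1.96) + Φ(−d/SE − 1.96), with d = p1 − 0.322

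| x | Patients moved (166 × 0.678 × x) | p1 | Odds ratio | SE | Rejection |
|---|---|---|---|---|---|
| 0 | 0 | 0.322 | 1.00 | 0.0614 | 5.0% |
| 2% | 2.3 | 0.336 | 1.06 | 0.0618 | 5.6% |
| 5% | 5.6 | 0.356 | 1.16 | 0.0624 | 8.4% |
| 10% | 11.3 | 0.390 | 1.35 | 0.0633 | 18.8% |

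Other normal approximations (pooled variance for the critical value with unpooled spread, or unpooled throughout) give 5.5–5.6%, 8.2–8.5% and 18.4–19.3%.

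**Opposite direction.** If instead 5% or 10% of anaemic patients with true loss are scored as no loss, p1 = 0.322 × 0.95 = 0.306 or 0.322 × 0.90 = 0.290. The odds ratio is then 0.93 or 0.86. With a real harmful association, the same error would pull the estimate towards 1.

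**The case against.** The strongest reply is that no harm is shown. The documents do not say that the caller knows the haemoglobin. The delegation tables, and Appendices 4 and 5 on scales and data collection, are not in the supplied text and could name the caller or fix the wording of the questions. ADL is a validated six-item scale with three fixed codes, and section 4.5 limits the calls to simple criteria. The misclassification shares come from no source, and at 2% the effect is negligible. Section 1.1 cites 93.0% of patients anaemic after surgery, so a general belief about anaemia would apply to almost everyone; bias needs the caller to know its severity.

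These points stand as limits on what can be claimed. They do not remove the gap: the main text requires no masking, so a study run exactly as written permits unmasked scoring and leaves no record of whether it occurred.

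A reader might go further and infer that callers will see the haemoglobin, or that the odds ratio will be inflated. The documents support neither. The expectation in section 1.1 concerns one department, whereas section 4.2 describes a multicentre study, and the same introduction reports cohorts and a transfusion review with no functional difference. A caller who knows that a patient was transfused might expect better recovery, which would push the other way.

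**Conclusion.** The concern holds in conditional form. The supplied text leaves the 6-month scorer unnamed and unmasked, on an outcome where one or two coding decisions can make an event. If scoring depends on knowledge of haemoglobin or transfusion, the primary odds ratio is biased and adjustment will not repair it. The direction depends on what callers expect.

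The size cannot be derived from the documents. The figures of 1.06, 1.16 and 1.35, with rejection in about 6%, 8% and 19% of studies, rest on an assumed one-directional error confined to patients below 10 g/dL. They show only that moving about 11 of 166 patients would matter and that moving about 2 would not. The change is worth making because it is cheap, and because what the caller knew cannot be reliably reconstructed afterwards.

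**What to change.** In section 4.1 (d and e) and section 4.5:

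1. State that the delegated caller uses a fixed-wording ADL/IADL script, on a call form that does not show haemoglobin, transfusion or iron data.
2. Require the ADL and IADL items to be asked and locked before the complication and re-hospitalisation questions. Under section 4.4 a transfusion after discharge means a new admission, so those answers may reveal one.
3. Where a centre's delegation log already names more than one person, use a caller who did not look after the patient in hospital.
4. Record at each call whether the caller knew the haemoglobin or transfusion status, and report this descriptively. Treat any analysis restricted to masked calls as exploratory: it rests on self-declared knowledge in a selected subset that is likely to differ by centre.

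The cost is a short script, a call form without the exposure fields and one extra tick-box. It needs no extra staff, visits or patients, and the planned 255 is unchanged. Masking will be incomplete in small centres, and a caller who also made the 1- or 3-month call may already have heard of a transfusion; the tick-box makes this visible. Patients, families and nursing home staff are not masked by any of this.
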